Evaluation of Wear Experience with Dailies TOTAL1 Multifocal[®] Contact lenses in Presbyopic Adults That Have Dropped out of Contact Lens Wear

Protocol number: 2023H0245

NCT number: NCT06053463

Version 2.0

18 October 2023

Evaluation of Wear Experience with Dailies TOTAL1 Multifocal[®] Contact lenses in Presbyopic Adults That Have Dropped out of Contact Lens Wear

[name], OD MS

The Ohio State University College of Optometry Innovation in Vision and Eye care Research Group - iVERG [name] [contact]

[name], OD, PhD

ProCare Vision Centers, Inc. [name] [contact]

Purpose

The purpose of this study to explore the wear experience in Dailies TOTAL1 Multifocal[®] contact lenses (Alcon, Fort Worth, TX, USA) in presbyopic adults who have previously dropped out of contact lens wear.

Study Overview

This open-label study is of presbyopic adults that have dropped out of contact lens wear. Participants whose habitual vision correction device is spectacles will be fit into Dailies TOTAL1 Multifocal[®] contact lenses. Participants will be assessed after 1 week of wear at a follow-up visit (Visit 2) to confirm a successful contact lens fit. Refitting will occur if necessary. Participants will return for a final visit after 4 weeks of wear that will include an Overall Wear Experience Survey.

Background and Rationale

Soft daily wear contact lenses are used by an estimated 40.9 million adults in the United States.[1] Contact lenses which are worn for daily wear are considered minimal risk by the FDA, and risks to wearers are minimized by proper lens care and hygiene. Daily disposable contact lenses do not require daily cleaning and overnight storage, which reduces the required amount of time to care for contact lenses. In addition, daily disposable contact lenses are associated with less lens deposits, which decreases associated comfort issues in lens wearers, including decreasing the risk of triggering Giant papillary conjunctivitis (GPC) and/or ocular allergic responses in patients.[2] Additionally, daily disposable contact lens wearers are not likely to expose their lenses to water and tend to have better lens hygiene since these lenses do not require daily cleaning. This is reflected in a study which found less superficial punctate staining and symptoms of dryness when comparing daily disposable contact lens wear with planned replacement lenses.[3]

Global contact lens prescribing for the first 20 years of this century show that the average age of contact lens wearers was 30.8 ± 13.9 years for males and 32.5 ± 14.3 years for females. Trend analysis for that

20 year period also revealed an increase in age of lens wearers and an incomplete provision of near contact lens corrections for contact lens wearing presbyopes.[4] The increasing age of lens wearers and the limited provision of corrections indicate an unmet need. In addition, many individuals discontinue contact lens wear once their eyes require presbyopic correction.[5] Reasons for this include dissatisfaction with comfort and/or vision[5].

Purpose

The purpose of this study is to evaluate the wear experience of people with presbyopia who previously dropped out of contact lens wear when fit with a Delefilcon A soft lens multifocal lens (Dailies TOTAL1 Multifocal, Alcon, Ft. Worth TX USA). We expect to enroll a relatively equal amount of former soft multifocal contact lens wearers who dropped out due to poor vision at distance or near and single vision wearers who dropped out due to poor near vision.

Key Endpoints

- 1. Visual Analog Scale survey of lens wear symptoms (comfort, dryness, vision) with contact lenses
- 2. Assessment of the participant's quality of life with the Dailies TOTAL1 Multifocal[®] contact lenses

Study Time Points

Visit 1 will occur to determine eligibility. The informed consent process will take place before the subject arrives on site via a phone call and REDCap e-consent. The participant will answer questions about their general and ocular health to further determine eligibility. Upon arriving, visual acuity and an assessment of ocular health will occur. Eligible subjects will complete a quality of life questionnaire via REDCap while wearing their progressive addition spectacles. A contact lens fitting will be completed to fit the participants in Dailies TOTAL1 Multifocal[®] contact lenses. The initial contact lens powers will be chosen following the manufacturer's fitting guide, and all subsequent changes will follow this guide, which is included in the appendix.

Visit 2 will occur 1 week (±3 days) after visit 1. Participants will return to the study site wearing the study provided contact lenses to complete distance and near visual acuity. Contact lens fit and movement will be assessed and the participants will be refit if necessary. If a refit is needed, an additional Visit 2 will be scheduled. This may be repeated until satisfactory fit is achieved.

Visit 3 will occur 1 month (±3 days) after the follow-up visit. Participants will return to the study site wearing the study provided contact lenses to complete distance and near visual acuity. Contact lens fit and ocular health will be assessed. The participants will complete the Overall Wear Experience Survey.

Surveys (which will be deployed in REDCap) will include:

Overall Wear Experience Survey

0-100 Scale:

- Quality of vision while watching television
- Quality of vision while using a smart phone
- Quality of vision while using the computer
- Quality of vision while dining out
- Quality of vision while playing sports
- Quality of vision while working out
- Quality of vision while reading a book/magazine/newspaper

- Overall quality of vision while wearing study lenses
- Overall comfort while wearing study lenses
- Overall satisfaction while wearing the study lenses

Exploratory endpoints

- How willing are you to continue wearing these contact lenses after the study?
- Would you recommend the study contact lenses to a friend?

Recruitment

Potential subjects may see posters placed on bulletin boards at The Ohio State University (OSU) or local eye care offices, emails to students, faculty and staff at OSU, online or paper ads, signs on the OSU buses, StudySearch, The College of Optometry website and the Innovation in Vision and Eye Care Research Group (iVERG) website. A search of the electronic medical records of The Ohio State College of Optometry may be done to identify possible subjects who may be contacted by email or phone with information about the study. A search of The OSU College of Optometry Research Database (2017H0032) will also be completed. Word of mouth referrals by study team members to OSU employees and friends may occur. Emails to alumni of the OSU College of Optometry may be sent for local doctors to notify eligible potential subjects about the study.

Inclusion criteria:

- 1. Ability to give informed consent.
- 2. Any gender.
- 3. Any racial or ethnic origin.
- 4. At least 38 years of age or older.

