This monadic study will report outcomes with descriptive statistics, and as such, no power calculation is necessary. A previous multifocal study with 20 subjects was conducted recently at this site which successfully recruited and studied presbyopic patients who wore progressive addition spectacles and fit them with multifocal lenses.

Data Management and Security

During the active stages of the study (recruitment to last measurement visit), all paperwork (consents, questionnaires and data forms) for each subject will reside in a subject folder for easy access throughout the study. The folders will reside in the limited-access research area, in a locked file drawer or cupboard. At the completion of the study or disenrollment of a subject the paperwork in the subject's folders will be reorganized into a regulatory binder (consents, W-9s) and a data binder (questionnaire and data forms) and will reside in an office in the limited-access research area. When the data analysis is completed and the study is considered complete, the binders will be stored in the secure Department or Office Clinical Research Area. Paperwork (questionnaire and data forms) for individuals who participate in the baseline visit but are not eligible to continue the study will be stored in the study regulatory binder in an office in the limited-access research area. An electronic file of potential subjects and a file of enrolled subjects with their contact information, as well as electronic files of collected data with the subject number, will reside on a limited-access shared drive with firewall and password protection and is restricted to individuals in the research team. Any electronic data files that contain PHI will be destroyed at the conclusion of the study.

Risks to Subjects and Mitigation

Although rare, a subject could experience eye pain, changes in vision, continued redness or irritation of the eye when inserting or learning to insert a contact lens. More likely transient blurring of vision (less than one minute) or mild, transient (less than a minute) stinging may occur.

Whenever wearing a contact lens, the possibility of eye pain due to scratching the eye or getting an infection is possible, but not common.

Adverse Events

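### Key Endpoint 1 includes dryness with contact lenses, but no assessment scheduled in the study lenses specifies a dryness item

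*Combined protocol and SAP*

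**What the plan says.** Key Endpoints, item 1, is a "Visual Analog Scale survey of lens wear symptoms (comfort, dryness, vision) with contact lenses". It names three symptoms and ties all of them to contact lens wear.

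Study Time Points then sets out what happens at each visit:

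- **Visit 1**, listed before the lens fitting: "Eligible subjects will complete a quality of life questionnaire via REDCap while wearing their progressive addition spectacles".
- **Visit 2**, in the study lenses: distance and near acuity, and then "Contact lens fit and movement will be assessed and the participants will be refit if necessary".
- **Visit 3**, in the study lenses: acuity, lens fit and ocular health, and then "The participants will complete the Overall Wear Experience Survey".

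The Overall Wear Experience Survey is itemised on a 0-100 scale. It has seven task-specific vision items, followed by "Overall quality of vision while wearing study lenses", "Overall comfort while wearing study lenses" and "Overall satisfaction while wearing the study lenses". Two exploratory questions follow, on willingness to keep wearing the lenses and on recommending them to a friend.

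Under Statistical Analysis and Power Calculation: "This monadic study will report outcomes with descriptive statistics".

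**The concern.** A key endpoint should trace to an item, on a named instrument, at a stated visit. For vision and comfort that trace can be made, provided the 0-100 survey is the Visual Analog Scale survey of Key Endpoint 1, which the protocol never says. For dryness there is nothing to trace to on any reading of the visit schedule.

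Visit 3 is the final visit and the only one with a survey scheduled in the study lenses. A dryness rating not collected then cannot be recovered later. The report would show a key endpoint with one component missing, and a reader could not tell an oversight in the survey from a result left out.

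**Working it through.** The plan gives no sample size, power or error rate for this endpoint, so there is no figure to reproduce. The check is a mapping of each component of Key Endpoint 1 to the assessments scheduled in the study lenses.

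**Step 1. Count the listed questions** (Overall Wear Experience Survey and Exploratory endpoints).

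- Task-specific vision: television, smart phone, computer, dining out, sports, working out, reading = 7
- Overall vision = 1, so vision items = 7 + 1 = 8
- Overall comfort = 1
- Overall satisfaction = 1
- Scaled items = 8 + 1 + 1 = 10
- Exploratory questions = 2
- All questions = 10 + 2 = 12, of which dryness = 0

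**Step 2. Map by component of Key Endpoint 1.**

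| Component | Items at Visit 3 |
|---|---|
| Vision | 8 |
| Comfort | 1 |
| Dryness | 0 |

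Two of the three named components have at least one item.

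**Step 3. Look for dryness at the other visits** (Study Time Points).

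| Visit | Patient-reported assessments scheduled in the study lenses | With a dryness item |
|---|---|---|
| 1 | 0 (the questionnaire is completed in spectacles) | 0 |
| 2 | 0 (acuity, fit and movement only) | 0 |
| 3 | 1 (Overall Wear Experience Survey) | 0 |

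The ocular health assessment at Visit 3 might record signs related to dryness. It is not a symptom survey, however, and it names no dryness measure.

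**Step 4. Look elsewhere in the document.** Dryness appears otherwise only in Background and Rationale, in a literature comparison of daily disposable with planned replacement lenses. The only content the protocol attributes to its appendix is the manufacturer's fitting guide.

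**Step 5. Can comfort stand in?** Key Endpoint 1 lists comfort and dryness separately, so the protocol itself treats them as distinct. A single overall comfort score cannot be split afterwards to give a dryness result.

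**The case against.** The strongest reply is that absence from the list is weak evidence of absence from the study. The list of REDCap surveys is introduced in the plural and in non-exclusive terms, yet it itemises only one. It omits the Visit 1 quality of life questionnaire, which certainly exists. Key Endpoint 2 implies a further quality of life assessment in the lenses, and that too has no named instrument or visit. If the Visual Analog Scale survey is separate from the Overall Wear Experience Survey, the count of 0 in 12 describes the wrong instrument. The defect would then be an unlisted survey, not a missing item.

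This stands as a limit on the claim. The documents show that no dryness item is specified; they do not show that none exists. It does not remove the problem, because a key-endpoint instrument that is not named, itemised or scheduled is itself a gap, and staff following the visit schedule would collect no dryness rating. The wider point also stands: neither key endpoint is explicitly mapped to an instrument and visit, and repairing dryness alone would leave Key Endpoint 2 unmapped.

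A second reply is that little is at stake. The study is single-arm and descriptive, and eligibility turns on having stopped lens wear for visual reasons, with or without discomfort. That is fair and it limits the severity. Even so, the sponsor chose to make dryness part of a key endpoint.

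**Conclusion.** The concern holds. Of 12 listed questions none addresses dryness, so one of the three components of Key Endpoint 1 has no specified measurement in the study lenses. Run as written, the study would have nothing to report for it.

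The loss is confined to that component. The vision results (8 items) and the comfort result (1 item) are unaffected, no estimate is biased, and no sample size depends on it. It should be fixed before data collection, but it does not threaten the study as a whole.

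The item count is certain. The conclusion about lost data assumes that the visit schedule is complete, that is, that no unlisted survey with a dryness item is given at Visit 2 or Visit 3.

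**What to change.** First, state which instrument is the Visual Analog Scale survey of Key Endpoint 1. Then take one of three routes:

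1. **If it is the Overall Wear Experience Survey**, say so in one sentence. Add one 0-100 item on overall dryness with the study lenses at Visit 3, worded in parallel with the comfort item. State its anchors and direction, since a high score could mean either more or less dryness. Report it descriptively beside comfort and vision.
2. **If it is a separate instrument**, name it, list its items including dryness, and assign it to a visit at which the study lenses are worn.
3. **If dryness is not meant to be measured**, remove it from Key Endpoint 1.

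The first route costs one REDCap item and one clarifying sentence. The second costs listing and scheduling the instrument at an existing visit. The third is a one-word deletion. None needs an extra visit or procedure.

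### Key endpoint 2, quality of life with the study lenses, has no identified in-lens measurement: the only quality-of-life questionnaire scheduled is completed in spectacles at Visit 1

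*Combined protocol and SAP*

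**What the plan says.** Key Endpoints lists two items. The first is "Visual Analog Scale survey of lens wear symptoms (comfort, dryness, vision) with contact lenses". The second is "Assessment of the participant's quality of life with the Dailies TOTAL1 Multifocal[®] contact lenses". Neither gives a visit or a summary score, and the second gives no instrument.

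Under Study Time Points, Visit 1 has this: "Eligible subjects will complete a quality of life questionnaire via REDCap while wearing their progressive addition spectacles". The fitting comes next in the text: "A contact lens fitting will be completed to fit the participants in Dailies TOTAL1 Multifocal[®] contact lenses". No further questionnaire is listed at that visit.

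Visit 2 consists of distance and near acuity, lens fit and movement, and a refit where needed. Visit 3 consists of acuity, lens fit, ocular health and one patient-reported instrument: "The participants will complete the Overall Wear Experience Survey". The Study Overview agrees: "Participants will return for a final visit after 4 weeks of wear that will include an Overall Wear Experience Survey".

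Statistical Analysis and Power Calculation says of the analysis only: "This monadic study will report outcomes with descriptive statistics, and as such, no power calculation is necessary". It names no quality-of-life score, visit or comparison.

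**The concern.** The endpoint concerns life in the study lenses, while the one measurement bearing that name is taken in the correction the lenses are meant to replace. If the schedule is carried out as written, one of the two key endpoints has no identified in-lens data, and the Visit 1 score has no identified in-lens counterpart. Visual acuity could still be compared within person, because it is recorded at every visit, but acuity is not quality of life.

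The remaining route is to call some part of the Visit 3 survey quality of life once the data are in. In an open-label, single-lens study with no prespecified score, that leaves the content of a key endpoint to be chosen with the results in view. The loss is also hard to repair: a participant who leaves Visit 3 without completing the questionnaire cannot supply that score later under the planned conditions.

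**Working it through.** The plan states no figure to reproduce, since it has no sample size, alpha or power. The check is whether endpoint 2 can be traced to a scheduled measurement.

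**Step 1: where the term occurs.** Quality of life appears twice in the document: in endpoint 2 and in the Visit 1 questionnaire. It is absent from Visits 2 and 3, the survey list, the exploratory questions and the statistical section.

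**Step 2: endpoint against schedule.**

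| Visit | Correction worn | Patient-reported instrument named | Called quality of life? |
|---|---|---|---|
| 1 | Progressive spectacles | Unnamed questionnaire | Yes |
| 2 | Study lenses | None | No |
| 3 | Study lenses | Overall Wear Experience Survey | No |

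In-lens visits with a quality-of-life questionnaire: 0 of 2.

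**Step 3: could the survey be the measure?** Its items, each scored 0 to 100, are:

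- vision during seven activities (television, smartphone, computer, dining out, sports, working out, reading): 7
- overall vision: 1
- overall comfort: 1
- "Overall satisfaction while wearing the study lenses": 1

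Vision items: 7 + 1 = 8. Vision or comfort items: 8 + 1 = 9. Total: 9 + 1 = 10. So 9 of 10 items lie in domains that endpoint 1 names, and one (satisfaction) lies outside them. None is labelled quality of life. The fit to endpoint 1 is itself incomplete, because endpoint 1 also names dryness and the survey has no dryness item.

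The content therefore does not settle the allocation. If the survey serves endpoint 1, endpoint 2 is left with at most the satisfaction item. If it serves endpoint 2, endpoint 1 loses the only survey the protocol itemises. If it serves both, the protocol does not say which items belong to which.

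**Step 4: could the survey be the Visit 1 questionnaire under another name?** Three items (overall vision, comfort and satisfaction) refer to the study lenses, which are not yet worn when that questionnaire is completed, so the two cannot be identical as printed. The seven activity items do not mention lenses and could be answered in spectacles. Because the Visit 1 questionnaire is not named and its items and scoring are not given, overlap can be neither shown nor ruled out.

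**The case against.** The best defence is that the survey is the endpoint 2 measure. Seven of its ten items ask about vision in everyday activities and one asks about satisfaction, which is close to vision-related quality of life. With no dryness item, it is not an obvious instrument for endpoint 1 either. This reading is plausible, and the absence of dryness does weaken any claim that the survey belongs to endpoint 1. It does not attach the survey to endpoint 2, and no sentence in the protocol does so.

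A second defence is that the survey list is open. It is introduced as a list of what the surveys will include, and it omits the Visit 1 questionnaire even though that is also deployed in REDCap. Absence from the list is therefore weak evidence. That is fair, but the gap lies in the Visit 3 schedule, which names one survey, and an open list of instruments does not place a questionnaire at a visit. The appendix is cited only for the manufacturer's fitting guide.

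A third defence is that the study is purely descriptive, ranks no endpoint as primary, and collects in-lens ratings of vision, comfort and satisfaction in any case. This limits the harm: no error rate or power is at stake, and the broad aim of describing wear experience has its survey. A descriptive study must still fix in advance which data describe each key endpoint.

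Finally, the endpoint asks for a level in lenses, not a change from spectacles, so a paired change goes beyond what the protocol promises. That stands. The change is a useful extra, and the in-lens score is what the endpoint requires.

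**Conclusion.** The concern holds. As written, 1 of 2 key endpoints has no identified in-lens measurement: there is one quality-of-life questionnaire at Visit 1 in spectacles, none at Visit 2 and none at Visit 3. This is more than missing detail, because following the schedule faithfully would not produce the endpoint under its own name.

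The conclusion rests on the protocol text alone. It does not assume that the survey is unsuitable as a quality-of-life measure, only that the protocol does not designate it as one. If the sponsor intended that designation, the defect is one of wording and allocation, and no new data are needed. If the sponsor intended to repeat the Visit 1 questionnaire, that repeat has to be scheduled before participants complete Visit 3.

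**What to change.** Choose one of two routes and write it into Key Endpoints, Study Time Points and the statistical section.

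1. **Repeat the questionnaire (preferred).** Name the quality-of-life questionnaire and its scoring. Add to Visit 3: *Participants will complete the same quality of life questionnaire as at Visit 1, while wearing the study lenses.* Report the Visit 3 score as endpoint 2, with the paired change from Visit 1 given descriptively; a 95% confidence interval is optional. The cost is a few minutes per participant, a short amendment and one more descriptive table. No extra visit is needed.
2. **Designate the existing survey.** State that the Overall Wear Experience Survey is the endpoint 2 measure, list which items count towards each endpoint, reword endpoint 2 to match, and state the purpose of the Visit 1 questionnaire. This needs only wording changes.

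Neither route calls for a power calculation.

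### The only survey of study-lens wear with a stated visit comes at Visit 3, after the refit loop, so people who wear the lens and leave earlier have no scheduled rating of it

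*Combined protocol and SAP*

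**What the plan says.** The survey is mentioned in two places, both at the end of the study. The Study Overview says "Participants will return for a final visit after 4 weeks of wear that will include an Overall Wear Experience Survey". Study Time Points says of Visit 3 "The participants will complete the Overall Wear Experience Survey", and times that visit as follows: "Visit 3 will occur 1 month (±3 days) after the follow-up visit".

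Before that, Visit 2 covers distance and near acuity and the lens itself: "Contact lens fit and movement will be assessed and the participants will be refit if necessary". It can recur: "If a refit is needed, an additional Visit 2 will be scheduled. This may be repeated until satisfactory fit is achieved". No maximum number of refits is given, and no rule for a fit that never succeeds.

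The one other questionnaire with a stated visit is at Visit 1: "Eligible subjects will complete a quality of life questionnaire via REDCap while wearing their progressive addition spectacles".

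Key Endpoints lists a "Visual Analog Scale survey of lens wear symptoms (comfort, dryness, vision) with contact lenses" and an assessment of "quality of life with the Dailies TOTAL1 Multifocal" lenses. No visit is attached to either there. The survey's comfort and vision items appear to serve the first of these, but the survey lists no dryness item. The willingness and recommendation questions stand under Exploratory endpoints, also without a visit.

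Consent and Confidentiality lets participants stop whenever they wish. Subject Dismissal removes those who miss a visit window or cannot give analyzable data. The analysis section promises descriptive statistics and does not mention an analysis set or missing data.

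**The concern.** The purpose is to describe the wear experience of presbyopic former wearers who are fitted with this lens. Inclusion criterion 8 admits only people who gave up lenses over vision, or over vision together with discomfort. Vision, comfort and satisfaction are what the survey rates. A participant who gives up again before Visit 3 may well do so for the same reasons, and that person's rating is the one the schedule does not collect.

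In a single-arm descriptive study there is no comparator arm in which a similar loss might offset this one. The survey means would describe people with a satisfactory fit who stayed, yet could be read as describing everyone fitted. The willingness question is the clearest case: those who have shown by leaving that they do not wish to continue have no scheduled occasion to answer it. Study records can show later how many left. They cannot show how those people would have rated the lens.

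**Working it through.** **No figure to reproduce.** The documents state no sample size, stopping rate or expected rating for this trial.

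**What each visit collects from the participant about the study lens**

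- Visit 1: a quality of life questionnaire in spectacles, so no rating of the lens.
- Visit 2 and any repeats: acuity, fit and movement. These are clinical measurements; no rating is listed.
- Visit 3: the Overall Wear Experience Survey.
- Exit before Visit 3: nothing described.

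**Time to the first scheduled rating, with no refit**

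- Visit 2 is at 7 ± 3 days, that is day 4 to day 10.
- Visit 3 is one month ± 3 days later. Taking a month as 28 days (the four weeks of the Study Overview) to 31 days gives 25 to 34 days.
- The first rating therefore falls between day 4 + 25 = 29 and day 10 + 34 = 44. Refits push it later, if the month runs from the last Visit 2.

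**Who can leave after wearing the lens and before that rating**

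- Those who stop voluntarily.
- Those whose fit is never satisfactory.
- Those dismissed for a missed visit window.

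Dismissal for unanalyzable data is a fourth route on paper, but Subject Dismissal says such problems usually show at screening. Those people would mostly have little or no wear to rate.

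**Bound on the mean.** Let f be the share of fitted participants with no survey, C the completer mean, and r the mean that the others would have given, between 0 and 100.

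All-fitted mean = (1 − f) × C + f × r

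As r runs from 0 to 100, this moves by 100 × f points, whatever C is. For assumed f of 5%, 10%, 20% and 30% the width is 5, 10, 20 and 30 points. Each person lost from n fitted adds 100/n points: 10 for n = 10, 5 for n = 20, 2.5 for n = 40. The 20 is the size of the earlier study at this site, used only as an example.

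**Overstatement under an assumed gap.** Completer mean minus all-fitted mean = f × (C − r). With an assumed gap of 20 to 40 points:

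| f | Overstatement (points) |
|---|---|
| 5% | 1 to 2 |
| 10% | 2 to 4 |
| 20% | 4 to 8 |
| 30% | 6 to 12 |

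The 10% row is 2 of 20: 2/20 × 20 = 2 and 2/20 × 40 = 4.

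**Willingness, only if scored yes or no.** Suppose 15 of 18 completers are willing (15/18 = 83%) and 2 of 20 fitted have no answer. The share over all fitted is 15/20 = 75% with both counted unwilling and 17/20 = 85% with both counted willing. The item's wording suggests a graded answer, in which case this calculation does not apply as it stands.

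**The case against.** The strongest reply is that the design is coherent as it is. Visit 2 exists to confirm a successful fit, and a rating after a month in a confirmed fit is a sensible target for an exploratory, descriptive study. Repeated refits also help retention. This stands as a legitimate choice, but the purpose is not worded that narrowly. Even on this reading, people who stop after a satisfactory fit are still unrated.

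The magnitude is assumed throughout, and the 100 × f width holds for any 0-100 score with missing values. That is correct. It limits how much weight the point can carry, though not the fact that the ratings are not scheduled.

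Missed windows may reflect scheduling alone, and staff are to make reasonable efforts to accommodate participants. That also stands: this group is less likely to be informative than failed fits and voluntary stops.

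Three stronger readings are tempting, and the documents do not support them:

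- *No lens rating before Visit 3 will be taken.* The quality of life endpoint and the dryness part of the symptom endpoint have no stated visit, and the survey list is open-ended. Either could be collected earlier; the plan does not say.
- *Dissatisfied participants are filtered out.* What must be satisfactory is the fit. A well-fitted but unhappy completer can still give low ratings.
- *The Visit 3 results are shown to be biased.* No stopping rate is given and nothing is known about how leavers would rate the lens, so only a plausible direction can be stated.

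**Conclusion.** The point holds as a gap in data collection. As written, people who wear the lens but stop, fail refitting or are dismissed for a missed window have no scheduled rating, and the survey results will describe participants with a satisfactory fit who completed. Given the entry criterion, the likely direction is towards results that look too favourable for all people fitted. The size cannot be derived from the documents: it is zero if everyone reaches Visit 3, and 1 to 12 points across the assumed losses and gaps tabulated above. If the untimed key endpoints turn out to be collected at Visit 2, the gap is smaller. Importance is minor to moderate: a cheap change worth considering, because the ratings cannot be recovered once people have left.

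**What to change.** When a participant who has worn the lenses stops, fails refitting or is dismissed, give the existing survey and the willingness question at that contact if it is in person, and otherwise by REDCap link. Tying it to the contact at which the exit becomes known matters, because staff cannot tell in advance which visit will be someone's last. Allow a not-applicable answer for activities not tried.

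In the report:

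- Show exit ratings in a separate table, because wear was shorter.
- Label the Visit 3 results as participants with a satisfactory fit who completed.
- Give the numbers fitted, refitted, satisfactorily fitted and completed, with reasons for stopping.
- Report willingness for completers and, using exit answers, for all fitted participants, on the item's own scale. Use willing/unwilling bounds for missing answers only if the item is scored yes or no, or a cut-off is set in advance.

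If the sponsor wants month-end ratings in confirmed fits only, one sentence in the purpose should say so, with the exit ratings kept as a supplement.

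The cost is a few sentences in an amendment and one added REDCap trigger, with no extra visits. The limits are that exit ratings reflect shorter wear, that some who stop will not answer, and that the Visit 3 means remain completer-only.
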